From Month 2 to Month 12, the investigational site will contact each subject by telephone or site visit for review of daily electronic reporting tool data and assessment of SAEs, AESIs, and antiviral medication (through Month 6).

A Data Monitoring Committee (DMC) will review safety data at intervals of a minimum of 3 months until all subjects have completed the GEN-003/placebo dosing period. Any additional meetings and the specific safety monitoring plan will be detailed in the DMC charter.

Efficacy Endpoints:

Primary:

- Genital herpes lesion rate (proportion of days with lesions present) in the 6-month period after the maintenance dose: Based on subject report of genital lesions via a daily electronic reporting tool

Secondary:

- Frequency of genital herpes recurrences in the 6-month period after the maintenance dose: Based on subject report of genital lesions via a daily electronic reporting tool
- Proportion of subjects genital herpes recurrence-free at 6 months after the maintenance dose: Based on subject report of genital lesions via a daily electronic reporting tool
- Time to first genital herpes recurrence in the 6-month period after the maintenance dose: Based on subject report of genital lesions via a daily electronic reporting tool
- Duration of genital herpes recurrences in the 6-month period after the maintenance dose: Based on subject report of genital lesions via a daily electronic reporting tool

Safety Endpoints:

- Reactogenicity
 - Local reactions: Pain, tenderness, swelling, redness
 - Systemic events: Fever, headache, chills, fatigue, nausea, vomiting, diarrhea, muscle aches
- AE, SAEs, AESIs, MAAEs

Number of Subjects Planned: Up to 90 subjects

Diagnosis and Main Criteria for Inclusion: Subjects who completed Study GEN-003-003 (completed all study visits including the Month 12 visit) and received all 3 doses of active GEN-003 (any dose combination), received the last dose of GEN-003 within 11 to 18 months, and reported data in daily electronic reporting period on at least 80% of days, and had no important protocol deviation.

Duration of Treatment: 1 dose

Test Product; Dose; and Mode of Administration: GEN-003 (60 µg of each antigen, GB208)

and GB217, 50 µg of MM2, and normal saline), administered as a 0.5 mL IM injection

Control Product; Dose; and Mode of Administration: Normal saline, administered as a 0.5 mL IM injection

Statistical Methods:

Sample Size: No formal sample size calculations were performed for this study.

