1.5.3 GEN-003-002a: Rollover Trial for Placebo Subjects Previously Enrolled into GEN-003-002 - A Randomized, Double-Blind, Factorial Study to Compare the Safety and Efficacy of Varying Combinations of GEN-003 and Matrix-M2 in Subjects with Genital HSV-2 Infection

Subjects who received placebo in Study GEN-003-002 were offered enrollment in this study of the same active dose combinations given in that study.

The study is complete; 37 subjects were enrolled. The low number of subjects per group precluded a meaningful inference about the effect of antigen or adjuvant dose on the clinical efficacy of the different dose combinations.

No AEs leading to discontinuation of dosing, SAEs, AESIs, or deaths occurred during the study. The most common local reactions during the 7 days after vaccination were pain and tenderness at the injection site, which occurred in most subjects. The most common systemic events were fatigue and muscle aches, which also occurred in most subjects. The incidence and severity of overall AEs and treatment-related AEs were similar across all dose groups.

Within the limitations of the small sample size, the safety profile of GEN-003 in this study was similar to previous studies.

1.5.4 GEN-003-002b: A Long-term Follow-up Study of Efficacy and Immunogenicity of GEN-003 in Subjects with Genital Herpes Simplex Virus Type 2 (HSV-2) Infection

Subjects who received at least 1 dose of GEN-003 (any dose combination) and had no important protocol deviations in Study GEN-003-002 were offered enrollment in this follow-up study to evaluate long-term efficacy and immunogenicity up to 48 months postdose. A total of 140 subjects have been enrolled, and the study is ongoing.

1.5.5 GEN-003-003: A Randomized, Double-blind Study to Evaluate a New Formulation of GEN-003 in Subjects with Genital HSV-2 Infection

Subjects aged 18 to 50 with documented diagnosis of genital HSV-2 infection for > 1 year were randomized in a 1:1:1 ratio to receive 3 IM doses of 1 of the following doses of a new GEN-003 formulation at intervals of 21 days:

- GEN-003: 60 µg each antigen + 50 µg MM2 (43 subjects)
- GEN-003: 60 µg each antigen + 75 µg MM2 (44 subjects)
- Placebo: (44 subjects)

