4 SUBJECT POPULATION

4.1 Inclusion Criteria

1. Completed Study GEN-003-003 (completed all study visits including the Month 12 visit)
2. Received all 3 GEN-003 doses (any dose combination) in Study GEN-003-003
3. Received last dose of GEN-003 within 11 to 18 months before the maintenance dose
4. Reported data in the daily electronic reporting period on at least 80% of days in Study GEN-003-003
5. Collected at least 45 swabs (of 56 total expected swabs) during the Month 11 to 12 swab collection period in Study GEN-003-003
6. Willing and able to provide written informed consent
7. Willing to perform and comply with all study procedures, including attending clinic visits as scheduled and completion of a daily electronic reporting tool
8. Postmenopausal (≥ 12 months with no menses without an alternative medical cause) or willing to practice a highly effective method of contraception that may include, but is not limited to, abstinence, sex only with persons of the same sex, monogamous relationship with a postmenopausal partner, monogamous relationship with vasectomized partner, vasectomy, hysterectomy, bilateral tubal ligation, licensed hormonal methods, intrauterine device (IUD), or use of a spermicide combined with a barrier method (e.g., condom, diaphragm) for 28 days before and 90 days after receiving the IP

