10.7 Primary Efficacy Endpoint – Genital Herpes Lesion Rate

Genital herpes lesion rates (the proportion of days with genital lesions present) in the 6-month period after the maintenance dose will be compared between treatment groups using the Wilcoxon rank sum test.

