### **5.2 Sample Size Justification**

Sample size in this study is dependent on the enrollment in GEN-003-003. No formal sample size calculations were performed for this study.

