### **5.3 Randomization**

Eligible subjects were randomized in a 1:1 ratio to receive 1 IM dose of GEN-003 (60 µg each antigen and 50 µg MM2) or placebo. Randomization was stratified on the basis of the GEN-003 dose received by the subject in Study GEN-003-003.

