## **11 EFFICACY ANALYSIS**

### **11.1 Genital Herpes Lesion Rate**

Lesion rate (days) is defined as number of days with lesions divided by the time period of follow-up for lesions (in days). The days with lesions will be collected continuously throughout the study via an electronic lesion diary, and lesion rates will be calculated for the following periods: Baseline and Day 1 to 183 (post-dosing). For the purposes of determining days with lesions, a diary entry of missing will be treated the same as a diary entry of “no,” except in the following case: if 1 or 2 consecutive instances of missing is flanked by “yes” values on both sides, those missing values will be treated as a “yes” value.

Lesion rate will be analyzed with descriptive summary tables for overall and individual lesion rates calculated for the periods noted above. Individual subject lesion rates will be compared for the active treatment group vs. placebo using the Wilcoxon rank sum test.

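### The primary lesion-rate test does not adjust for each subject's GEN-003-003 lesion rate, and the SAP leaves both the baseline lesion rate and the quantity tested undefined

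*SAP*

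**What the plan says.** - **Primary test.** SAP 11.1: "Individual subject lesion rates will be compared for the active treatment group vs. placebo using the Wilcoxon rank sum test". Protocol 10.7 says the rates "will be compared between treatment groups using the Wilcoxon rank sum test", and the synopsis agrees. No covariate or stratum is named.
- **Size.** SAP 5.2: "No formal sample size calculations were performed for this study". The synopsis gives "Number of Subjects Planned: Up to 90 subjects", and SAP 5.2 ties the number to enrolment in GEN-003-003.
- **Parent-study diary.** Inclusion criterion 4 (Protocol 4.1): "Reported data in the daily electronic reporting period on at least 80% of days in Study GEN-003-003".
- **Baseline.** SAP 11.1 calculates lesion rates for a baseline period and for Days 1 to 183, without saying which days make up the baseline. SAP 5.5.2 sets the default baseline as Day 1 of GEN-003-005. The Table 14.2.3.1 shell has blocks for baseline, Days 1-183 and change from baseline, with its single p-value directly beneath the change block.
- **Other use of parent-study data.** Randomisation was stratified by the GEN-003 dose received in GEN-003-003 (SAP 5.3). Protocol 10.2 allows optional sensitivity analyses using the original treatment assignment. Neither uses the earlier lesion rate.

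**The concern.** How often a person has recurrences is likely to differ between people and to persist over time. If so, a subject's earlier lesion rate predicts the later one, and a test that leaves it out carries avoidable noise. The trial has no sample-size basis and cannot grow beyond the parent study, so precision matters. The earlier rate was fixed before randomisation, so adjusting for it does not bias the comparison of arms.

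The second difficulty is one of definition. The diary in this trial starts on Day 1, so a multi-day pre-dose rate can only come from GEN-003-003, yet the SAP's default baseline points elsewhere. The text of SAP 11.1 describes a test on rates, while the table shell can be read as a test on change. These are different tests with different power, and two programmers could produce different primary p-values from the same plan.

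**Working it through.** The plan states no power or sample size, so there is no figure to reproduce.

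**Inputs from the documents**
- Parent-study active arms: 43 and 44 subjects (Protocol 1.5.5), 87 in all. Allocation is 1:1, so about 43 per arm at most. Two subjects in each active arm stopped dosing for safety reasons: 87 − 4 = 83, or about 41 per arm.
- The only between-group lesion-rate effect reported: 4.5% against 7.9% of days, printed as a 41% reduction with P < 0.05 and no SD (Protocol 1.5.5). It compares the three-dose series with placebo, not a maintenance dose with placebo.
- Mean recurrences over 6 months and Kaplan-Meier recurrence-free percentages (Protocol Table 1).

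**Assumptions**: two-sided 5% level (none is stated for this test), the standardised effect d, and the correlation r between parent-study and post-dose rates.

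**Step 1. What the documents imply about r.** They report no correlation. Suppose recurrence counts are negative binomial with a stable subject rate, mean m per 6 months and dispersion k. Then P(0) = (1 + m/k)^(−k), and the correlation of 12-month with 6-month counts is (2m²/k) / √[(m + m²/k)(2m + 4m²/k)].

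| Arm | m | Recurrence-free | k | Implied correlation |
|---|---|---|---|---|
| Placebo | 2.7 | 10% | 7.4 | 0.34 |
| Placebo | 2.7 | 13% | 3.8 | 0.49 |
| 50 µg MM2 | 2.1 | 22% | 2.4 | 0.54 |
| 50 µg MM2 | 2.1 | 29% | 1.3 | 0.69 |
| 75 µg MM2 | 1.9 | 31% | 1.3 | 0.67 |
| 75 µg MM2 | 1.9 | 36% | 0.9 | 0.74 |

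One Table 1 thus gives 0.34 to 0.74. These are counts, not lesion rates. The method treats Kaplan-Meier estimates as proportions, and drift in a subject's rate would lower every value.

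**Step 2. Power by formula, n = 43 per arm.** As an anchor, the d that just reaches p = 0.05 with 43 against 44 is 1.96 × √(1/43 + 1/44) = 0.42. Power = Φ(d / (s√(2/n)) − 1.96), with s = 1 unadjusted, s = √(1 − r²) adjusted, and s = √(2(1 − r)) for a change score with equal pre and post variances.

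| r | Unadjusted | Adjusted | Gain (points) | Change score |
|---|---|---|---|---|
| 0.2 | 49.5% | 51.1% | 1.6 | 33.7% |
| 0.3 | 49.5% | 53.2% | 3.7 | 37.7% |
| 0.4 | 49.5% | 56.5% | 7.0 | 42.8% |
| 0.5 | 49.5% | 61.4% | 11.9 | 49.5% |
| 0.6 | 49.5% | 68.2% | 18.7 | 58.6% |
| 0.7 | 49.5% | 77.8% | 28.3 | 71.0% |

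The change score falls below the unadjusted test when 2(1 − r) > 1, that is, when r < 0.5. It never beats adjustment in this approximation, because 2(1 − r) − (1 − r²) = (1 − r)² ≥ 0. Across d = 0.2 to 0.8, r = 0.2 to 0.7 and 30 to 45 per arm, the gain from adjustment runs from about 0.3 to 28 points. At d = 0.8 and 43 per arm it never exceeds 3.9.

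**Step 3. Simulation, Wilcoxon against rank analysis of covariance.**
- 41 per arm, 41% reduction, recurrences drawn from Table 1 figures, 12 months of parent diary assumed, with and without drift, 3,000 trials per scenario. Power was 44.0 → 53.5%, 34.2 → 40.6%, 32.5 → 45.4%, 24.2 → 32.5%, 60.6 → 69.7% and 46.9 → 51.5%: gains of 4.6 to 12.9 points. Rank correlations were 0.36 to 0.57. Type I error was 4.7 to 5.9% across both tests.
- 43 per arm, 41% reduction, assumed mean rate 6%, between-subject CV 0.9, 4-day outbreaks, 1,500 runs. Power was 52.3 → 53.6%, 53.1 → 56.1%, 54.9 → 59.8% and 52.7 → 63.3%, at rank correlations of about 0.17, 0.28, 0.38 and 0.51: gains of about 1 to 11 points.
- The second set-up with a 20% reduction: gains of about 0.5 to 4 points. A further run gave 0 to 4.

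**The case against.** The strongest reply is that an unadjusted Wilcoxon test is valid, so this is a preference about efficiency and not the correction of an error. That stands. The parent study also used the Wilcoxon test for recurrence number and duration, so keeping it helps comparison. The trial is Phase 2, makes no sizing claim, and was cut back when the sponsor stopped development. These points limit the weight of the concern but do not remove it.

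A reader might infer that the SAP ignores baseline altogether. It does not: it plans a baseline rate and a change from baseline, and may intend its p-value for the change. The documents support only that the baseline is undefined and the tested quantity unclear.

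A reader might also infer that the parent-study rate is a strong predictor. No correlation is reported, and the model-implied range of 0.34 to 0.74 is too wide to settle it.

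The cost is also more than SAP wording. The test is written into Protocol 10.7 and the synopsis, and Protocol 11.6 requires a written amendment with IRB/EC submission.

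**Conclusion.** The concern holds in a limited form. The primary test as written makes no use of a pre-randomisation lesion history that criterion 4 secures for every eligible subject. The SAP does not define its baseline lesion rate or say whether the p-value tests the rate or the change.

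With about 41 to 43 per arm, adjustment gains roughly 1 to 13 points of power at a 41% reduction and about 0 to 4 points at 20%. In no simulated scenario did it lower power, and type I error stayed near 5%. If the shell is followed and change is tested, power falls below that of the unadjusted test when r is under about 0.5.

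It is tempting to quote a fixed loss of 5 to 13 points. By formula, that needs r of about 0.34 to 0.52 together with d = 0.42 and 43 per arm, and none of these is established. The 41% figure is a primary-series effect. Every subject here has already had the full series, and no document gives an expected maintenance effect.

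**What to change.** Make these changes before the Month 6 interim analysis, when SAP 5.4.2 unblinds the sponsor and study team:

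1. In SAP 11.1, define the baseline lesion rate as the GEN-003-003 diary rate over a fixed window, for example all diary days after the last parent-study dose, and exempt it from the Day 1 default in SAP 5.5.2.
2. Make the primary test a rank analysis of covariance: rank the post-dose rate and the baseline rate, regress the first on the second, and compare arms on the residuals. Preferably include the prior-dose randomisation stratum as well.
3. In Table 14.2.3.1 and its per-protocol counterpart, place the p-value against the Days 1-183 rate and leave the change block descriptive.
4. Keep the unadjusted Wilcoxon test as supportive, which preserves a link to the parent study's results.
5. Amend Protocol 10.7 and the synopsis to match.

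The cost is one merge with the GEN-003-003 diary data, the SAP and shell edits, a protocol amendment, and slightly less direct comparability with the parent study's Wilcoxon results. No new data are collected.

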## **11.2 Frequency of Genital Herpes Recurrences**

The frequency of genital herpes recurrences in the 6-month period after the maintenance dose will be calculated as the number of recurrences reported using the daily electronic lesion diary, and will be summarized by mean, SD, median, and range. The median frequencies of recurrences will be compared between treatment groups using the Wilcoxon rank sum test.

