10.8 Secondary Efficacy Endpoints

10.8.1 Frequency of Genital Herpes Recurrences

The frequency of genital herpes recurrences in the 6-month period after the maintenance dose will be calculated as the number of recurrences reported and summarized by mean, SD, median, and range. The median frequencies of recurrences will be compared between treatment groups using the Wilcoxon rank sum test.

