Appendix 1 Schedule of Events

Study Day/Month Window (days)	Study Vaccine (GEN-003/Placebo) Dosing Period		
	Maintenance Dose		
	Day 1	Day 8	Day 29/Month 1
		± 3	± 3
	Clinic Visit	Clinic Visit	Clinic Visit
Informed consent	X		
Medical history	X		
Serum (S) / urine (U) pregnancy test	U		S
Concomitant medication and vaccine assessment	X	X	X
Eligibility criteria check	X		
Weight	X		
Serum for research purposes	X	X	X
PBMCs for research purposes ^a	X	X	X
Randomization	X		
GEN-003/placebo dosing ^b	X		
Distribution (D) / review (R) of Diary Card	D	R	
Instruction in daily electronic reporting tool	X		
Daily electronic reporting tool	Subject will report the presence or absence of genital lesions, and severity of genital herpes symptoms on each day from Day 1 through Month 6.		
Review of daily electronic reporting tool data		X	X
EQ-5D-5L	Subject will complete the EQ-5D-5L on each day of the first recurrence after the maintenance dose through Month 6.		
AE (including SAEs, AESIs, MAAEs) assessment	X	X	X

AE = adverse event; AESI = adverse event of special interest; EQ-5D-5L = EuroQoL – 5 Domains – 5 Levels; MAAE = medically attended adverse event; PBMC = peripheral blood mononuclear cell; SAE = serious adverse event.

a At selected sites only

b After confirmation of no febrile illness or other acute illness for the past 48 hours

Study Day/Month	Follow-up Period							
	Month 2	Month 3	Month 4	Month 6	Month 8	Month 9	Month 10	Month 12
Window (days)	Day 57 ± 7 days	Day 85 ± 7 days	Day 113 ± 7 days	Day 169 ± 14 days	Day 225 ± 14 days	Day 253 ± 14 days	Day 281 ± 14 days	Day 337 ± 14 days
	Phone Contact	Clinic Visit	Phone Contact	Clinic Visit	Phone Contact	Clinic Visit	Phone Contact	Clinic Visit
Daily reporting tool	Subject will report the presence or absence of genital lesions and severity of genital herpes symptoms on each day from Day 1 through Month 6.							
Review of daily electronic reporting tool data	X	X	X	X				
EQ-5D-5L	Subject will complete the EQ-5D-5L on each day of the first recurrence after the maintenance dose through Month 6.							
SAE/AESI/MAAE assessment	X	X	X	X	X	X	X	X
Antiviral and vaccine use assessment	X	X	X	X				

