## 2 STUDY OVERVIEW

This study is a randomized, double-blind, placebo-controlled clinical trial of GEN-003 in subjects who have received previous doses of GEN-003. Subjects who completed Study GEN-003-003 and received all 3 doses, reported data in daily electronic reporting period on at least 80% of days, and had no important protocol deviation in that trial were offered enrollment in this study. Subjects who met all inclusion and no exclusion criteria and provided written informed consent for this study were randomized within 11 to 18 months after the last active GEN-003 dose in a 1:1 ratio to receive 1 intramuscular (IM) dose (the maintenance dose) of GEN-003 or placebo. Randomization was stratified on the basis of the GEN-003 dose received by the subject in Study GEN-003-003.

Subjects were to use a daily electronic tool for reporting the presence or absence of genital herpes lesions and severity of genital herpes symptoms from Day 1 until the Month 6 visit.

Subjects were to complete the EuroQol – 5 Domains – 5 Levels (EQ-5D-5L) questionnaire on each day of the first recurrence after the maintenance dose through Month 6.

Local reactions and systemic events were to be recorded for the first 7 days after the maintenance dose on a paper Diary Card; if any event was ongoing after Day 8, it was to be followed until resolution. All adverse events (AEs) and concomitant medications were to be recorded from Day 1 to Day 29/Month 1. After Day 29/Month 1 to the end of the study, only serious AEs (SAEs), AEs of special interest (AESIs), medically attended AEs (MAAEs), antiviral medications, and vaccines were to be recorded. All AEs were to be graded in accordance with the Toxicity Grading Scale for Healthy Adult and Adolescent Volunteers Enrolled in Preventive Vaccine Clinical Trials from Grade 1 (mild) to Grade 4 (life-threatening).

From Month 2 to Month 6, the investigational site was to contact each subject monthly by telephone or site visit for review of daily electronic reporting tool data and assessment of SAEs, AESIs, and antiviral medication use (through Month 6).

A Data Monitoring Committee (DMC) was to review safety data at intervals of a minimum of 3 months until all subjects have completed the GEN-003/placebo dosing period. Any additional meetings and the specific safety monitoring plan were to be detailed in the DMC charter.

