## **5.5 Data Handling**

### **5.5.1 Method for Handling Missing Data**

No imputation of missing data will be performed. All available safety and efficacy data will be included in data listings and summaries.

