## **11.5 Duration of Genital Herpes Recurrences**

Mean lesion outbreak duration is defined as the average number of days with lesions per outbreak for those who have lesion outbreaks (recurrences).

Mean lesion outbreak duration will be presented in a similar descriptive summary table as done for lesion rate as described above. Individual subject mean outbreak duration will be summarized by treatment arm over 6 months (Days 1 to 183) after the maintenance dose. A Wilcoxon rank sum test will be used to test the hypothesis that the median mean lesion outbreak durations are the same between treatment groups at 6 months after the maintenance dose.

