**Table 14.2.4.1: Frequency of Recurrences at 6 Months After Maintenance Dose by Treatment Group**  
mITT Population

Statistic	GEN-003 60 ug/ M2 50 ug N=xx	Placebo N=xx	P-value[1]
Number of Recurrences at 6 Months after Maintenance Dose			0.xxxx
n	xx	xx	
Mean	xx.xx	xx.xx	
SD	xx.xxx	xx.xxx	
Median	xx.xx	xx.xx	
Min, Max	xx.x, xx.x	xx.x, xx.x	

Note: Recurrences refer to subject-reported recurrences.  
[1]P-value based on Wilcoxon rank sum test.

Program:

Date Produced: mm/dd/yy

Programming Notes:

- Number this table 14.2.4.1 and produce a similar table (14.2.4.2) for the PP population

[Sponsor]

Protocol: [Protocol number]

page x of y

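### Recurrence frequency is analysed as a raw count with no allowance for days observed, so an early leaver without a recurrence scores the same 0 as a complete lesion-free diary

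*SAP*

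**What the plan says.** The definition is a plain count in both documents. SAP 11.2 states that the frequency "will be calculated as the number of recurrences reported using the daily electronic lesion diary". Protocol 10.8.1 has it "will be calculated as the number of recurrences reported and summarized by mean, SD, median, and range". The test follows in SAP 11.2: "The median frequencies of recurrences will be compared between treatment groups using the Wilcoxon rank sum test". The shell for Table 14.2.4.1 has one variable, "Number of Recurrences at 6 Months after Maintenance Dose", with no row for days observed and no category for subjects who stopped early. Table 14.2.4.2 repeats it for the per-protocol population.

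Who is counted, and for how long:

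- SAP 4.1 keeps every randomized and dosed subject in the mITT population. Protocol section 8 does not replace withdrawals.
- SAP 5.5.1: "No imputation of missing data will be performed".
- SAP section 2 has subjects report "severity of genital herpes symptoms from Day 1 until the Month 6 visit". Protocol Appendix 1 places that visit at "Day 169 ± 14 days".
- SAP 11.5 describes the period as "over 6 months (Days 1 to 183) after the maintenance dose". SAP 11.2 speaks only of a 6-month period and gives no day range.

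**The concern.** A count of recurrences grows with the time a subject is watched. If it is ranked without regard to that time, leaving early looks like doing well. A subject who leaves on Day 20 with no outbreak ties for the best rank with a subject who completed a lesion-free diary.

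The SAP does not treat that subject this way elsewhere. Table 14.2.5.1 puts a recurrence-free early leaver under Unknown and excludes Unknown from the chi-square test. SAP 5.5.5 censors the same subject for time to first recurrence. SAP 11.2 has no counterpart.

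At stake is the first-listed secondary efficacy endpoint. If one arm loses more subjects, that arm can appear to have fewer recurrences when the true rates are equal. A real benefit can be hidden if placebo loses more.

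**Working it through.** The plan states no sample size, power, alpha or dropout rate, so it has no figure to reproduce. The check is arithmetic on follow-up, then a simulation under stated assumptions.

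**1. Follow-up among completers.** The visit window is 169 − 14 = Day 155 to 169 + 14 = Day 183. Against Days 1 to 183, a Day 155 visit covers 155/183 = 84.7% and a Day 169 visit covers 169/183 = 92.3%.

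**2. Expected raw count by days observed.** Take 2.7 per 183 days, using the parent study's placebo mean (Protocol Table 1) as an illustrative rate. Expected count = 2.7 × days/183.

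| Last diary day | Expected count |
|---|---|
| 183 | 2.70 |
| 169 | 2.49 |
| 155 | 2.29 |
| 85 (leaver) | 1.25 |
| 29 (leaver) | 0.43 |

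**3. What a zero means.** Assume gamma-Poisson counts with shape 1.5, so P(0) = (1 + m/1.5)^−1.5 for expected count m.

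- Day 20: m = 2.7 × 20/183 = 0.295 and P(0) = 1.197^−1.5 = 0.76.
- Day 183: m = 2.7 and P(0) = 2.8^−1.5 = 0.21.

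A zero by Day 20 says little and a zero by Day 183 says a lot. The planned test ranks them equally.

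**4. Rejection rate with identical arms.** Assumptions not in the documents: two-sided 5% level; true mean 2.4 per 183 days in both arms; shape 1.5; Month 6 visits uniform over Days 155 to 183 except in the first row; leavers exit uniformly over Days 8 to 154; 4,000 trials per scenario. The 45 per arm comes from the planned maximum of 90, allocated 1:1.

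| Dropout GEN-003 / placebo | Mean counts | Raw-count Wilcoxon | Wilcoxon on per-subject rate |
|---|---|---|---|
| None, all followed to Day 183 | 2.40 / 2.40 | 5.0% | 5.0% |
| None, visits spread | 2.22 / 2.21 | 4.5% | 4.7% |
| 10% / 10% | 2.10 / 2.10 | 4.8% | 4.6% |
| 15% / 5% | 2.05 / 2.16 | 5.8% | 5.1% |
| 20% / 5% | 1.98 / 2.16 | 6.8% | 5.2% |
| 30% / 5% | 1.87 / 2.15 | 10.1% | 5.7% |

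Simulation error near 5% is about ±0.7 points (1.96 × √(0.05 × 0.95/4000)).

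A further run at 45 per arm added the negative binomial model with log-days offset, its dispersion fixed at the true value. At 20%/5% the raw count rejected 6.8% and the model 4.8%. At 30%/10% the figures were 9.5% and 5.5%. Other runs of 30%/10%, with 40 per arm and mean 2.7, gave about 8% and 9.2% for the raw count. In the latter run the per-subject rate test gave 5.8%.

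**5. Size of the false gap.** At 20%/5% the means differ by 2.16 − 1.98 = 0.18. The parent study's difference was 2.7 − 2.1 = 0.6, so the gap is 0.18/0.6 = 30% of it.

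**6. True means 2.1 vs 2.7.** Power with full follow-up is 17.0%. On raw counts it becomes 26.2% at 20%/5% dropout and 7.8% at 5%/20%. On per-subject rates it is 19.8% and 11.9%.

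**The case against.** The strongest reply is that the bias needs unequal follow-up and nothing in the documents shows that it will occur. Subjects must have completed every parent-study visit through Month 12 and reported on at least 80% of diary days (Protocol 4.1). There is one dose, and missed entries trigger reminders and site contact (Protocol 6.1). At 10% vs 5% dropout the raw-count test rejects about 5.5%. This stands, and it limits the size. It does not exclude unequal loss: in the parent study Grade 3 reactions within 7 days of any of three doses occurred in 51.2% on this dose and 13.6% on placebo (Protocol 1.5.5). A written rule costs little.

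It may also be said that the no-imputation rule would lead an analyst to leave such subjects out. The SAP does not say so for this endpoint. Nor does the per-protocol analysis settle it: Table 14.2.1 measures diary compliance only up to the Month 6 visit or discontinuation, so on that definition an early leaver can reach 100%.

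Stronger readings that the documents do not support:

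- *That early Month 6 visits bias the comparison.* In a randomized, blinded trial visit timing should be similar in both arms. On its own it lowers both means and leaves the error rate near 5%.
- *That the reported means are wrong by 10%.* At a true 2.7 with 5% dropout in both arms the mean is about 2.43, and (2.70 − 2.43)/2.70 = 10%. But 2.70 − 2.49 = 0.21 of that comes from measuring a Day 169 visit against Day 183, a window that SAP 11.2 does not state. Only 2.49 − 2.43 = 0.06 comes from dropout.
- *That dividing each subject's count by days and ranking the result solves the problem.* The Day 20 leaver with no outbreak has 0/20 = 0 and keeps the best rank. With one outbreak the value is 183/20 = 9.15, near the worst.
- *That every other endpoint handles short follow-up cleanly.* SAP 11.1 divides lesion days by follow-up time, but the lesion-rate shells divide by days in the observation period.

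The 2.7 is itself uncertain, since Protocol Table 1 does not say whether it was adjusted for exposure.

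**Conclusion.** The concern holds in this form: the plan states a rule that takes no account of days observed, and that rule biases the between-arm comparison if follow-up differs by arm. Under assumed dropout of 20%/5% to 30%/10% with identical arms, a nominal 5% test rejects about 7% to 9.5% of the time. With equal dropout, mildly unequal dropout (10%/5%) or visit timing alone it stays near 5%. A reader might infer that the result will be biased. The documents do not support that, because they give no dropout rate by arm.

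The figures rest on gamma-Poisson counts with shape 1.5, uniform leaving times, and leaving unrelated to recurrences. This is a secondary endpoint in a trial with no formal sample size, so the change is worthwhile but not critical. The clearest reason for it is internal: the same subject is Unknown in Table 14.2.5.1 and, as written, a 0 in Table 14.2.4.1.

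**What to change.** In Protocol 10.8.1 and SAP 11.2, compare recurrence rates with a negative binomial model with log(observed diary days) as offset, and report the rate ratio with its 95% CI. Define observed diary days with the same start and cut-off as the count. The days with entry already derived for Table 14.2.1 can serve. Say how a dosed subject with no diary day is reported, since the offset is then undefined.

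In Tables 14.2.4.1/.2, add a row for days observed by arm. Keep the raw count and its Wilcoxon test as descriptive or supportive. A Wilcoxon test on the per-subject rate may be shown as a sensitivity analysis, as it brings the error rate back to about 5% to 6%. It should not be called equivalent, because it leaves the zero-count early leaver at the best rank.

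The cost is a short SAP change, one derived variable and one model. The downside is a distributional assumption, and the dispersion must be estimated, whereas the check above fixed it at its true value. The offset also assumes that the rate while observed represents the rest of the period, so it does not remove bias if subjects leave because of their recurrences.
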